Once the EP procedure is complete, the subject will be transferred from the operating room to a hospital room, where they will stay overnight. Measurements will be made during this period, but not while the subject is being transferred. Once the subject is situated in the hospital room, the CoVa™ 2 Sensor will be applied to the subject and connected to the external power supply in the same manner as described above. Then measurements will commence according to the same duty cycle as described above.

The patient will continuously wear the CoVa™ 2 system until they are discharged for a period of about 24 hours. During this period, data from the sensor will be sent to the Gateway and Cloud-based System, and then analyzed retrospectively.

During the course of the study, scientists at toSense will use the Data Analytics Software to process measurement information from CoVa™ 2, with a focus of proving or disproving the study's primary hypothesis, i.e. when the CoVa™ 2 Sensor is used before, during, and after an EP procedure, can it successfully measure patients, indicate the efficacy of the EP procedure, show any signs of patient decompensation or complications, and allow a patient to be discharged relatively early?

More detailed analyses will investigate the study's secondary objectives, i.e.: 1) can measurements made by the CoVa™ 2 Sensor be successfully made before, during, and after an EP procedure; 2) is there correlation between parameters such as volume status, heart rate and arrhythmia, SV, and CO before, during, and after an EP procedure; 3) does RF ablation during an EP procedure interfere with CoVa™ 2 Sensor measurements?; 4) does a shock during a DC cardioversion interfere with CoVa™ 2 Sensor measurements?; and 5) is the usability of the CoVa™ 2 Sensor adequate before, during, and after an EP procedure suitable for clinicians?

Upon completion of the study, a report will be drafted describing the above-described information. The report may evolve into a peer-reviewed publication if this is determined by the PI to be an appropriate course of action.

This measurement protocol will be performed for a period of at approximately 6 months.

Study Endpoints

Primary Study Endpoints

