The primary endpoint will be if at least 50% of subjects studied in this trial are able to be discharged relatively early from the hospital if they are monitored with CoVa™ 2, as determined through a retrospective analysis. A detailed retrospective statistical report will be the determining factor in meeting this success criteria.

Study Enrollment and Withdrawal

Inclusion Criteria

In order to be eligible to participate in this study, an individual must meet all of the following criteria:

1. Patients with arrhythmias and other cardiac conditions that are scheduled for EP procedures.
2. Subject is over 22 years of age at the time of consenting
3. Subject and/or legally authorized representative is willing to undergo the informed consent process prior to enrollment in the study

Exclusion Criteria

An individual who meets any of the following criteria will be excluded from participation in this study:

1. Pregnant subjects
2. Subjects who are participating in another clinical study that may affect the results of either study

3. Subjects who are unwilling or unable to wear the sensor (and electrodes) for a period of up to 14 hours
4. Subjects who are considered by the principle investigator to be medically unsuitable for study participation

Vulnerable Subjects

Vulnerable subjects will not be utilized in this study. In the case of a vulnerable population patient being identified; they will not be included in the study or analysis..

Strategies for Recruitment and Retention

No NYULMC media will be used to recruit subjects. Subjects that are scheduled for an EP procedure and meet the inclusion criteria will be approached for enrollment.

Subjects will be consented in a quiet and private environment. Subjects will be given the opportunity to take the written consent form home to review overnight.

Use of DataCore/Epic Information for Recruitment Purposes

This study will utilize EPIC to identify subjects. Once potential subjects have been identified, the study team will notify the treating physician (TP) that they have patients eligible to participate. The study team will obtain approval from the treating physician to approach the eligible patient for the study.

Duration of Study Participation

The total duration of study participation is about 1.5 days. This includes:

Written Informed Consent Process: 1 day

Study Procedure: 1 day

Measurement prior to EP Procedure: 1-3 hours

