Measurement after EP procedure: Patient will be measured until they are discharged from hospital (approximately 24 hours).

Subjects may be contacted for a follow-up interview.

Total Number of Participants and Sites

This is a single-site study. Recruitment will end when approximately 20 participants are enrolled. It is expected that approximately 20-30 participants will be recruited in order to produce 20 evaluable participants.

Reasons for Withdrawal or Termination

Participants are free to withdraw from participation in the study at any time upon request. An investigator may terminate participation in the study if:

- Any clinical adverse event (AE), laboratory abnormality, or other medical condition or situation occurs such that continued participation in the study would not be in the best interest of the participant
- The participant meets an exclusion criterion (either newly developed or not previously recognized) that precludes further study participation

Handling of Participant Withdrawals or Termination

Withdraw criteria:

- The Principle Investigator will review whether a withdrawal of a subject affects the success criteria of the study. A subject may be replaced if it is determined that more subjects are needed based on this criterion

Premature Termination or Suspension of Study

This study may be temporarily suspended or prematurely terminated if there is sufficient reasonable cause. Written notification, documenting the reason for study suspension or termination. If the study is prematurely terminated or suspended, the PI will promptly inform the IRB and will provide the reason(s) for the termination or suspension.

Circumstances that may warrant termination or suspension include, but are not limited to:

- Determination of unexpected, significant, or unacceptable risk to participants
- Demonstration of efficacy that would warrant stopping
- Insufficient compliance to protocol requirements
- Data that are not sufficiently complete and/or evaluable
- Determination of futility

Study may resume once concerns about safety, protocol compliance, data quality are addressed and satisfy the IRB.

Study Agent (Study drug, device, biologic, vaccine etc.) and/or Procedural Intervention

Study Agent(s) and Control Description

Acquisition

toSense will ship CoVa™ 2 systems directly to the Electrophysiology supplies team at the NYU medical center.

New York Medical Center
[name],
[name]
New York, NY
10016

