- The rights of a research subject to revoke their authorization for use of their PHI.

In the event that a subject revokes authorization to collect or use PHI, the investigator, by regulation, retains the ability to use all information collected prior to the revocation of subject authorization. For subjects that have revoked authorization to collect or use PHI, attempts should be made to obtain permission to collect at least vital status (i.e. that the subject is alive) at the end of their scheduled study period.

Participant confidentiality is strictly held in trust by the participating investigators and study staff. This confidentiality is extended to cover testing of biological samples and genetic tests in addition to the clinical information relating to participants. Therefore, the study protocol, documentation, data, and all other information generated will be held in strict confidence. No information concerning the study or the data will be released to any unauthorized third party.

Study members, and representatives of the IRB may inspect all documents and records required to be maintained by the investigator, including but not limited to, medical records (office, clinic, or hospital) and pharmacy records for the participants in this study.

The study participant's contact information will be securely stored at each clinical site for internal use during the study. At the end of the study, all records will continue to be kept in a secure location for as long a period as dictated by local IRB and Institutional regulations.

Study participant research data, which is for purposes of statistical analysis and scientific reporting, will be transmitted to and stored at NYU Langone Medical Center. This will not include the participant's contact or identifying information. Rather, individual participants and their research data will be identified by a unique study identification number. The study data entry and study management systems used by clinical sites and by NYU Langone Medical Center research staff will be secured and password protected. At the end of the study, all study databases will be de-identified and archived at the NYU Langone Medical Center.

Data Collection and Management Responsibilities

Data collection is the responsibility of the clinical trial staff under the supervision of the site PI. The investigator is responsible for ensuring the accuracy, completeness, legibility, and timeliness of data.

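### The protocol combines in-study work on the primary hypothesis with an open efficacy stop, which does not fit its single retrospective analysis and can inflate the chance of passing

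*Protocol*

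**What the plan says.** Four places in the protocol bear on this.

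- **Description of Study Design** gives the timing, which is while the study is running, and the party: "scientists at toSense will use the Data Analytics Software to process measurement information". It gives the purpose as "with a focus of proving or disproving the study's primary hypothesis". That hypothesis is then spelled out in four parts, the last being whether the device allows relatively early discharge.
- **Premature Termination or Suspension of Study** lists, among the circumstances that may end the study, "Demonstration of efficacy that would warrant stopping" and "Determination of futility". Neither has a number or timing of looks, a boundary or a named decision-maker.
- **Primary Study Endpoints** sets success as "at least 50% of subjects studied in this trial are able to be discharged relatively early", determined retrospectively, and makes a retrospective statistical report decisive. The Endpoint row of the Protocol Summary also makes that report decisive. The Brief Summary and Description of Study Design call the analysis retrospective too, and the latter has the report drafted when the study is complete.
- **Total Number of Participants and Sites** gives about 20 evaluable participants. The Methodology row of the Protocol Summary says there is no randomization or blinding.

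**The concern.** One set of passages describes a single analysis after the data are in. The other has the primary question worked on while subjects are still being enrolled, and allows the study to end because efficacy has been shown. The two do not fit together, and nothing in the protocol says which governs.

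This matters because the success rule is a bare observed proportion. In a sample of 10 or 15 such a proportion swings widely, and stopping when it happens to be high keeps the favourable swing. Two things follow. A device whose true early-discharge rate is below 50% passes more often than it would with one analysis at 20 subjects. The reported proportion is also too high on average.

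**Working it through.** **Inputs from the protocol.** N = 20; pass if the observed proportion is at least 50%, that is 10 or more of 20; efficacy stop allowed with no rule. The protocol states no error rate, power or assumed true rate, so there is no figure of its own to reproduce.

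**Assumptions, not in the protocol.** True early-discharge rate p of 30%, 40% or 45%; the look schedules shown below; and an efficacy stop that uses the same 50% threshold, declaring a pass at the first look that meets it and otherwise continuing to 20.

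**One look at 20.** P(pass) = Σ C(20,k) p^k (1−p)^(20−k) over k = 10 to 20. At p = 0.40 this is 0.2447.

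**Looks at 10 and 20, p = 0.40.** P(pass) = P(X10 ≥ 5) + P(X10 ≤ 4 and X20 ≥ 10) = 0.3669 + 0.0550 = 0.4219.

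**Looks at 15 and 20, p = 0.40.** At 15 subjects, 50% requires 8 or more. P(pass) = P(X15 ≥ 8) + P(X15 ≤ 7 and X20 ≥ 10) = 0.2131 + 0.0761 = 0.2892.

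**A look after every subject from the 10th.** The same exact enumeration, removing each path at the first look where the count is at least half the number of subjects, gives 0.4721 at p = 0.40.

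Probability of passing, with the ratio to a single look in brackets:

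| True rate | 20 only | 15, 20 | 10, 20 | Every subject from 10th |
|---|---|---|---|---|
| 30% | 4.8% | 6.8% (×1.42) | 16.3% (×3.40) | 19.1% (×3.97) |
| 40% | 24.5% | 28.9% (×1.18) | 42.2% (×1.72) | 47.2% (×1.93) |
| 45% | 40.9% | 45.6% (×1.12) | 57.7% (×1.41) | 62.8% (×1.54) |

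**Bias of the estimate, looks at 10 and 20, p = 0.40.** If the study stops at 10 the estimate is X10/10. If it continues, its expectation given X10 is (X10 + 4)/20. The deviations of X10 from 4 average to zero overall, so the bias is E[(X10 − 4); X10 ≥ 5] × (1/10 − 1/20). The expectation is 4 × P(X9 ≥ 4) − 4 × P(X10 ≥ 5) = 4 × 0.5174 − 4 × 0.3669 = 0.602. The bias is 0.602/20 = 0.030, so a true 40% is reported as 43.0% on average. With a look after every subject from the 10th, enumeration gives 43.3%.

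**The case against.** The strongest reply is that the protocol repeatedly calls the analysis retrospective, makes a retrospective report decisive and has it drafted on completion. It nowhere provides for a running count, or for a pass when that count crosses 50%. The termination list is generic and is tied neither to the endpoint nor to the manufacturer, and the IRB must be told the reason for any termination. Interim rules are commonly left to a statistical analysis plan, which may exist.

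Much of this stands as a statement of likely intent. It does not remove the conflict. Retrospective analysis of each subject's stored data is compatible with enrolment continuing, and the protocol itself places the work during the study and grants the efficacy stop without pointing to any rule. This is text that permits something, not a detail left for later.

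A reader might infer more than this, and three such readings fail.

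- *That the manufacturer decides when to stop, or will adjust the analysis to early subjects.* The protocol gives the manufacturer the processing, not the stopping decision, and describes no such adjustment. The absence of a stated software version or classification lock is a detail that a statistical analysis plan could supply.
- *That the false-pass chance doubles.* It can under some assumptions, but one late look at 15 gives only ×1.18 at a true 40%, and nothing in the table doubles it at 45%.
- *That removing the stop cures the success rule.* One look at 20 still passes 24.5% of the time at a true 40% and 40.9% at 45%, because the rule is an observed proportion with no confidence bound. That is a separate matter.

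**Conclusion.** The point holds as a conflict within the protocol with a statistical consequence. In-study processing directed at the primary hypothesis, together with an efficacy stop that has no looks or boundary, permits an unadjusted early stop and sits badly with the single retrospective report that is meant to decide success.

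The size depends on true rates, looks and a stopping threshold that the protocol does not give. Over the cases shown, the chance of passing with a true rate below 50% rises by a factor of about 1.1 (true 45%, one extra look at 15) to about 4 (true 30%, a look after every subject from the 10th). The upward bias is about 3 percentage points at a true 40% when looks start at the 10th subject. The direction is not in doubt for any stop of this kind. The conclusion is about what the text allows, not about what any party intends.

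**What to change.** 1. In Premature Termination or Suspension of Study, delete the efficacy ground. Leave the safety, compliance and data-quality grounds unchanged.
2. In Description of Study Design and Primary Study Endpoints, state that the primary early-discharge proportion is computed once, after the last evaluable subject is discharged, and that processing during the study is not used to tally that endpoint.

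This brings the text into line with the retrospective report that the protocol already makes decisive. At N = 20 it returns the pass probabilities to the single-look column: 4.8%, 24.5% and 40.9% at true rates of 30%, 40% and 45%. The change is wording only. Its price is that results on the hypothesis wait until the end of a study of about 6 months.

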Objectives	The primary objective of this study is to show that, when used before, during, and after an EP procedure, CoVa™ 2 is able to successfully measure vital signs, waveforms, and hemodynamic parameters from patients, indicate the efficacy of the EP procedure, and show any signs of patient decompensation or complications. An additional objective of this study is to show that, through use of CoVa™ 2, patients can be discharged relatively early from the hospital after undergoing an EP procedure.
Methodology	No randomization or blinding methods will be used for this study.
Endpoint	The primary endpoint will be if at least 50% of subjects studied in this trial are able to be discharged relatively early from the hospital if they are monitored with CoVa™ 2. A detailed retrospective statistical report will be the determining factor in meeting this success criteria.
Study Duration	Approximately 6 months
Participant Duration	Up to 7 days (until hospital discharge).
Duration of IP administration	N/A
Population	Approximate sample size: 20 subjects. Subjects are those which need an EP procedure,, including atrial fibrillation and SVT, pacemaker or ICD implant.
Study Sites	NYU Medical Center Electrophysiology [name]
Number of participants	20 subjects across one site

Description of Study Agent/Procedure	Subjects will be measured with CoVa™ 2 before and after an EP procedure.
Reference Therapy	N/A
Key Procedures	EP
Statistical Analysis	Statistical comparison (e.g. correlations) of measurements made before, during, and after the EP procedure to prove or disprove the above-mentioned study hypothesis.

Schematic of Study Design

1 Key Roles

Principle Investigator
[name]
[contact]

Sub Investigator
[name]
[contact]

Introduction, Background Information and Scientific Rationale

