toSense's CoVa™ 2 features a body-worn Sensor, Gateway, and Web-based System. The Sensor perform measurements by non-invasively sensing and processing single-lead ECG and TBI waveforms. Algorithms on the device processes these two waveforms to measure HR, HRV, RR, TEMP, FLUIDS, SV, and CO.

The Sensor has a form factor similar to a conventional necklace, with the electronics built into its strands and base. To make a measurement, a pair of customized disposable Electrodes—each featuring two electrode regions—snaps into a magnetic interface on the backside of the base and then attaches to the patient's chest. The Sensor is typically used for measurement periods less than 5 minutes but can also be used for longer periods (e.g. several hours or days).

Using a Bluetooth™ transceiver, the Sensor wirelessly transmits measurement information from the patient to a Gateway, such as a tablet computer or mobile phone running the Android operating system. These systems receive information from the Sensor, and then forward it to the Web-based System through either a local-area network (e.g., network based on 802.11), or a wide-area cellular network (e.g. AT&T). The Web-based System displays information and can forward it to a third-party system through a web-services interface.

CoVa™ is FDA-cleared (K160899) for the measurements described above.

Clinical Data to Date

See attached documents.

Known Potential Risks

Electrodes placed on the body may cause a slight redness or irritation. In rare cases, there is an allergic reaction or sensitivity to the adhesive that is used to stick the electrode patch. However, the adhesive that is used is not unique to this study, and is used in many medical applications. Discomfort could also occur when the adhesive patches are removed.

Known Potential Benefits

Subjects involved in this study will receive additional monitoring and may be discharged from hospital earlier as a result.

Objectives and Purpose

Primary Objective

When used before, during, and after an EP procedure, CoVa™ 2 is able to successfully measure vital signs, waveforms, and hemodynamic parameters from patients, indicate the efficacy of the EP procedure, and show any signs of patient decompensation or complications. Related to this primary objective is the goal of answering the following questions: Can data generated by CoVa™ 2 allow patients to be discharged from the hospital relatively early and monitored at home?

Secondary Objectives (if applicable)

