In addition to the primary study objective, investigate the following questions: 1) can measurements made by the CoVa™ 2 (particularly stroke volume (SV), cardiac output (CO), fluid status, arrhythmia detection, and basic vital signs) be successfully made before, during, and after an EP procedure?; 2) is there correlation between CoVa™ 2-measured parameters (particularly volume status, heart rate and arrhythmia, SV, and CO) before, during, and after an EP procedure?; 3) does RF ablation during an EP procedure interfere with CoVa™ 2 measurements?; 4) does a 200-300 Joule shock during a DC cardioversion procedure interfere with CoVa™ 2 measurements?; and 5) is the CoVa™ 2's usability suitable for hospital clinicians?

Description of Study Design

Study subjects scheduled for an EP procedure who have signed an informed consent form (ICF) will be admitted to the study. Prior to the EP procedure (e.g. in a hospital room or operating room at NYU Medical Center), an employee of NYU will prep the subject's skin with an alcohol wipe, apply the CoVa™ 2 Sensor using a pair of disposable electrodes, connect it to the Gateway Device using Bluetooth®, and ensure that it is transmitting information from the CoVa™ 2 Sensor through the Gateway Device to the Cloud-based System. All transmitted information will be de-identified. All subjects will continue to be monitored with standard of care equipment.

Once this data pathway is verified, measurements will be made from the subject for a period of approximately 2 hours prior to the EP procedure. More specifically, measurements will be made continuously for a period of about 90 seconds, and then, as described above, information will be transferred from the CoVa™ 2 to the Gateway Device, and from the Gateway Device to the Cloud-based System. This process will take roughly 120 seconds. Once it is complete, this 'duty cycle' will be repeated for the duration of the 2-hour period, i.e. measurements will again commence for a period of about 90 seconds, and then paused for about 120 seconds while data is wirelessly transmitted as described above.

Measurements will be temporarily halted as the subject is moved into the operating room and prepped for the EP procedure. Prior to the procedure, the CoVa™ 2 sensor will be attached to an external power supply as described above. Once the procedure is started, measurements will be made in the same manner as described above.

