The PI will confirm prior to enrollment that each subject qualifies for the study. The eligible subject will be approached by the research team. All patients willing to participate will personally sign and date the latest IRB approved version of the consent form. Written and verbal versions of the participant information and informed consent will be presented to the participants detailing no less than: the exact nature of the study; the implications and constraints of the protocol; the known side effects and any risks involved in taking part. It will be clearly stated that the participant is free to withdraw from the study at any time for any reason without prejudice to future care, and with no obligation to give the reason for withdrawal. The participant will be allowed as much time as wished to consider the information, and the opportunity to question the Investigator, their general practitioner or other independent parties to decide whether they will participate in the study. Written Informed Consent will then be obtained by means of participant dated signature and dated signature of the person who presented and obtained the informed consent. A copy of the signed Informed Consent will be given to the participants. The original signed form will be retained at the study site, in a research binder maintained by the study team in a locked cabinet. All documents will be stored safely in confidential conditions. On all physical and electronic study-specific documents, other than the signed consent, the participant will be referred to by a study participant number/code, not by name.

Visit 2 (Day of EP procedure)

- Ensure the subject has no additional questions regarding the study
- Once the subject has been prepped for surgery, apply the sensor to the subject's upper chest using the toSense approved electrodes
- Connect the device to the power source
- Study participant will be assigned a study number/code

- All data transmitted by the CoVa2 device will be de-identified.
- Run several test measurements on the sensor to ensure that the device is actively measuring on the subject
- Explain to the subject that the sensor will measure for a 90 seconds period, with 120 second pause in between measurements
- Measurements will not be made while the subject is transferred to and from the surgery room
- Measurements will be made until the patient is discharged

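### The claim that CoVa 2 can show whether the EP procedure worked is judged from CoVa 2 readings, with no independent record of the procedural result

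*Protocol*

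**What the plan says.** The Protocol Summary (Objectives) and the Primary Objective section both ask that CoVa 2 "indicate the efficacy of the EP procedure, and show any signs of patient decompensation or complications". The Description of Study Design repeats this as part of the primary hypothesis.

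The same section says how the hypothesis is to be decided: "scientists at toSense will use the Data Analytics Software to process measurement information from CoVa™ 2, with a focus of proving or disproving the study's" main hypothesis. The Protocol Summary (Statistical Analysis) gives the method: "Statistical comparison (e.g. correlations) of measurements made before, during, and after the EP procedure to prove or disprove the above-mentioned study hypothesis". The second of the Secondary Objectives has the same shape and asks: "is there correlation between CoVa™ 2-measured parameters (particularly volume status, heart rate and arrhythmia, SV, and CO) before, during, and after an EP procedure".

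Two other sources of information are mentioned. The Description of Study Design says "All subjects will continue to be monitored with standard of care equipment", and Duration of Study Participation says "Subjects may be contacted for a follow-up interview". Neither is given a role in the analysis.

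**The concern.** To say that a device indicates efficacy is to claim a relation between its readings and whether the procedure worked. Testing that needs both quantities. The stated comparison uses the readings in three periods, and the procedural result does not enter it.

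Readings can move around an EP procedure for reasons that have nothing to do with its success, such as sedation, fluids and bed rest. The study has one arm and no blinding, so the design offers no other way to tell these explanations apart. At stake is a statement on part of the primary hypothesis, in a report that may become a publication, which the data could neither support nor contradict.

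**Working it through.** The protocol gives no figure to reproduce for this part of the hypothesis: no significance level, effect size, SD or procedural success rate. The first check is therefore of the text.

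**Is the procedural result collected or used?**
- Description of Study Design: schedules CoVa 2 measurements in three periods. No procedural result is recorded.
- Visit 2, up to discharge: covers applying the sensor, cycles of measurement and pause, and a final transmission. No procedural result is recorded.
- Standard-of-care monitoring: continues, but is not named as study data or as a comparator.
- EPIC: named for identifying and screening subjects only.
- Follow-up interview: optional, with no stated content or use.
- Population: mixes AF, SVT, pacemaker and ICD procedures. Success is not defined for any of them.

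**What does a before/after comparison show when change is unrelated to success?** The 20 subjects come from the protocol. The two-sided paired 5% t-test and the size of the shift are my assumptions.
- The critical value on 19 degrees of freedom is 2.093. The noncentrality is d × √20, where d is the mean change divided by the SD of the change.
- d = 0.3: noncentrality 1.34, significant in 25% of trials.
- d = 0.5: noncentrality 2.24, significant in 56% (56–57% in simulation).
- d = 0.8: noncentrality 3.58, significant in 92%.

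In simulation the results at 0.5 and 0.8 SD were the same, within simulation error, for true success rates of 0%, 50% and 95%. This must be so, because success does not enter the test.

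**What does a comparison that uses the result show?** With the same 0.5 SD shift, unrelated to success, and 2, 4 or 6 failures among 20, a two-sample contrast on one parameter is significant in about 5% of trials. The like-for-like comparison is therefore about 56% against 5%, each for one parameter.

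**What could 20 subjects show once the result is recorded?** The success rates below are assumed. P(fewer than 2 failures) = s^20 + 20(1 − s)s^19.

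| Success rate s | Expected failures | P(fewer than 2 failures) | Lower 95% limit if every expected failure is flagged, 0.025^(1/f) | Power for a 1 SD difference |
|---|---|---|---|---|
| 80% | 4 | 0.012 + 0.058 = 0.07 | 0.40 | 40% |
| 90% | 2 | 0.122 + 0.270 = 0.39 | 0.16 | 25% |
| 95% | 1 | 0.358 + 0.377 = 0.74 | 0.03 | 15% |

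Even with the result recorded, this part of the hypothesis can be described but not proven.

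**The case against.** **There is no pass rule.** A reader might infer that any peri-procedural shift would count as showing efficacy. The protocol does not say that. It names a comparison, with correlations as an example, and sets no test, level or criterion for this part. The paired test above is only an illustration. What stands is that nothing in the plan guards against such a reading.

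**Other data are not barred.** The text does not say that CoVa 2 readings are the sole input, and a retrospective analysis could draw on routine records. An analysis plan, which is not shown, might arrange this. That is fair, and it is why the fix is cheap. But the protocol itself names the comparison and the data for deciding the hypothesis, and the result to be indicated is in neither. This goes beyond detail left for later.

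**CoVa 2 records an ECG.** After a rhythm procedure, whether the presenting arrhythmia persists is more informative than a generic shift, and the simulation leaves this out. This stands: the readings are not empty of information about success. The device's rhythm reading is still not checked against any independent record.

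**The size is easily overstated.** One could set the chance that at least one of seven parameters shifts (89–100% at 0.5 SD) beside the 5% above. That is not like for like, because the success/failure contrast on any of seven is significant in about 21–30% of trials.

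**Little power is gained.** This is true, and it argues for description rather than a test. A contrast pooled over procedures with different meanings of success should not be a decision criterion.

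**Conclusion.** The point holds as a gap between the claim and the data named to decide it. The primary objective and hypothesis include indicating efficacy, the stated analysis compares CoVa 2 readings across periods, and the procedural result is not recorded independently of the device. Followed as written, the plan can neither support nor refute this part.

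The illustration (about 56% against 5% for one parameter) rests on an assumed 0.5 SD shift and an assumed paired 5% test. The textual finding needs neither assumption.

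A reader might also infer that the trial's success criterion is undermined. It is not on this ground: the only numerical criterion is that at least 50% of subjects could be discharged early, and this part does not feed it. The matter should be corrected, but it affects what may be claimed about efficacy and not that threshold.

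**What to change.** Change the Protocol Summary (Statistical Analysis) and the Description of Study Design as follows:

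1. State that the operator's recorded acute result and the rhythm before and after will be copied from the existing procedure report and standard-of-care ECG, and fixed before CoVa data are viewed.
2. Report by procedure type, descriptively and with exact intervals, how CoVa heart rate, HRV and ECG rhythm agree with that record.
3. State that a before/after change in CoVa readings alone will not be reported as indicating efficacy.
4. Report this part as not assessable if too few procedures lack the recorded result, with the minimum number set in advance.

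The cost is some wording and a few chart items per subject that routine care should already produce. No procedure or subject is added. The downside is that this part may often be not assessable: at an assumed 95% success rate, about 74% of 20-subject samples have fewer than two failures, and splitting by procedure type thins the numbers further.
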